**Study Day 399 ( $\pm 2$  days; 7 day after Vaccination #4)**

1. Perform basic history and focused physical examination (including injection site), emphasizing examination of any acute complaints.
2. Record vital signs (blood pressure, temperature, and heart rate).
3. Record AEs and concomitant medications, if applicable.
4. Obtain approximately 5.0 mL of blood anti-Pfs230 antibody ELISA, and standard membrane feeding assay (SMFA).

**Study Day 406 ( $\pm 7$  day; 14 days after Vaccination #4)**

1. Perform basic history and focused physical examination (including injection site), emphasizing examination of any acute complaints.
2. Record vital signs (blood pressure, temperature, and heart rate).
3. Record AEs and concomitant medications, if applicable.
4. Obtain approximately 17.0 mL of blood for CBC with differential and platelet count, ALT, creatinine, malaria blood smear, malaria PCR, anti-Pfs230 antibody ELISA, standard membrane feeding assay (SMFA) and transcriptional analysis.

**Study Day 420 ( $\pm 7$  days; 28 days after Vaccination #4)**

1. Perform basic history and focused physical examination, emphasizing examination of any acute complaints.
2. Record vital signs (blood pressure, temperature, and heart rate).
3. Record AEs and concomitant medications, if applicable.

**Study Day 448 ( $\pm 7$  days; 56 days after Vaccination #4)**

1. Perform basic history and focused physical examination, emphasizing examination of any acute complaints.
2. Record vital signs (blood pressure, temperature, and heart rate).
3. Record AEs and concomitant medications, if applicable.
4. Obtain approximately 6.0 mL of blood for malaria blood smear, malaria PCR, anti-Pfs230 antibody ELISA, standard membrane feeding assay (SMFA).

**Study Day 504 ( $\pm 7$  days; 112 days after Vaccination #4)**

1. Perform basic history and focused physical examination, emphasizing examination of any acute complaints.
2. Record vital signs (blood pressure, temperature, and heart rate).
3. Record AEs and concomitant medications, if applicable.

4. Obtain approximately 6.0 mL of blood for malaria blood smear, malaria PCR, anti-Pfs230 antibody ELISA, standard membrane feeding assay (SMFA).

**Study Day 546 (±28 days; 154 days after Vaccination #4)**

1. Perform basic history and focused physical examination, emphasizing examination of any acute complaints.
2. Record vital signs (blood pressure, temperature, and heart rate).
3. Record AEs and concomitant medications, if applicable.
4. Obtain approximately 7.0 mL of blood for malaria blood smear, malaria PCR, anti-Pfs230 antibody ELISA, standard membrane feeding assay (SMFA) and transcriptional analysis.
5. Scheduled unblinding of VU
  - a. If received Pfs230D1M-EPA/ASO1 offer meningitis comparator vaccination

**Study Day 644 (±56 days; 252 days after Vaccination #4)**

1. Perform basic history and focused physical examination, emphasizing examination of any acute complaints.
2. Record vital signs (blood pressure, temperature, and heart rate).
3. Record AEs and concomitant medications, if applicable.
4. Obtain approximately 6.0 mL of blood for malaria blood smear, malaria PCR, anti-Pfs230 antibody ELISA, standard membrane feeding assay (SMFA).

**Study Day 728 (±56 days; 336 days after Vaccination #4)**

1. Perform basic history and focused physical examination, emphasizing examination of any acute complaints.
2. Record vital signs (blood pressure, temperature, and heart rate).
3. Record AEs and concomitant medications, if applicable.
4. Obtain approximately 6.0 mL of blood for malaria blood smear, malaria PCR, anti-Pfs230 antibody ELISA, standard membrane feeding assay (SMFA).

## Appendix C: Toxicity Tables

### Local Reactogenicity Grading

Local Reaction to Injectable Product	Mild (Grade 1)	Moderate (Grade 2)	Severe (Grade 3)	Potentially Life Threatening (Grade 4)
Pain at site	Does not interfere with activity	Repeated use of non-narcotic pain reliever > 24 hours or interferes with activity	Any use of narcotic pain reliever or prevents daily activity	ER visit or hospitalization
Erythema/Redness at site				
>15 years of age	2.5 – 5 cm	5.1 – 10 cm	> 10 cm	Necrosis or exfoliative dermatitis
≤ 15 years of age	≤ 2.5 cm in diameter	> 2.5 cm in diameter with < 50% surface area of the extremity segment involved (e.g., upper arm or thigh)	≥ 50% surface area of the extremity segment involved (e.g., upper arm or thigh)	Potentially life-threatening consequences (e.g., abscess, exfoliative dermatitis, necrosis involving dermis or deeper tissue)
Induration/Swelling at site				
>15 years of age	2.5 – 5 cm and does not interfere with activity	5.1 – 10 cm or interferes with activity	> 10 cm or prevents daily activity	Necrosis
≤ 15 years of age	≤ 2.5 cm in diameter	> 2.5 cm in diameter with < 50% surface area of the extremity segment involved (e.g., upper arm or thigh)	≥ 50% surface area of the extremity segment involved (e.g., upper arm or thigh)	Potentially life-threatening consequences (e.g., abscess, exfoliative dermatitis, necrosis involving dermis or deeper tissue)
Bruising at site				

>15 years of age	2.5 – 5 cm	5.1 – 10 cm	> 10 cm	Necrosis or exfoliative dermatitis
≤ 15 years of age	≤ 2.5 cm in diameter	> 2.5 cm in diameter with < 50% surface area of the extremity segment involved (e.g., upper arm or thigh)	≥ 50% surface area of the extremity segment involved (e.g., upper arm or thigh)	Potentially life-threatening consequences (e.g., abscess, exfoliative dermatitis, necrosis involving dermis or deeper tissue)
Pruritus at Site	Does not interfere with activity	Repeated use of medication > 24 hours or interferes with activity	Prevents daily activity	ER visit or hospitalization
Limitation of Arm Movement	Does not interfere with activity	Repeated use of medication > 24 hours or interferes with activity	Prevents daily activity	ER visit or hospitalization

Abbreviations: ER, emergency room.

 The definitions provided in the table are modified versions taken from the FDA Guidance for Industry “Toxicity Grading Scale for Healthy Adults and Adolescent Volunteers Enrolled in Preventive Vaccine Clinical Trials” dated September 2007 and DAIDS Table for Grading the Severity of Adult and Pediatric Adverse Events version 2.1 July 2017.

 In addition to grading the measured local reaction at the greatest single diameter, the measurement should be recorded as a continuous variable.

 Induration/Swelling should be evaluated and graded using the functional scale as well as the actual measurement.

**Vital Sign AE Grading**

Vital Signs	Mild (Grade 1)	Moderate (Grade 2)	Severe (Grade 3)	Potentially Life Threatening (Grade 4)
Fever (°C) (°F)	38.0 – 38.4 100.4 – 101.1	38.5 – 38.9 101.2 – 102.0	39.0 – 40 102.1 – 104	> 40 > 104
Tachycardia - beats per minute; at rest + calm				
Adult (≥13 yo)	101 – 115	116 – 130	> 130	ER visit or hospitalization for arrhythmia
Pediatric (≤ 12 yo)	121 – 135	136 -- 150	>150	ER visit or hospitalization for arrhythmia
Bradycardia - beats per minute; at rest + calm				
Adult (≥13 yo)	50 – 54	45 – 49	< 45	ER visit or hospitalization for arrhythmia
Pediatric (≤ 12 yo)	55 -- 59	50 – 54	< 50	ER visit or hospitalization for arrhythmia
Hypertension (systolic) -mm Hg; at rest + calm				
Adult (≥13 yo)	141 – 150	151 – 155	> 155	ER visit or hospitalization for malignant hypertension
Pediatric (≤ 12 yo)	131 -- 140	141 -- 150	> 150	ER visit or hospitalization for malignant hypertension

Hypertension (diastolic) -mm Hg; at rest + calm				
Adult (<math>\geq 13</math> yo)	91 – 95	96 – 100	> 100	ER visit or hospitalization for malignant hypertension
Pediatric (<math>\leq 12</math> yo)	81 -- 90	91 – 95	> 95	ER visit or hospitalization for malignant hypertension
Hypotension (systolic) -mm Hg; at rest + calm				
Adult (<math>\geq 13</math> yo)	85 – 89	80 – 84	< 80	ER visit or hospitalization for hypotensive shock
Pediatric (<math>\leq 12</math> yo)	80 – 84	75 – 79	< 75	ER visit or hospitalization for hypotensive shock

Abbreviations: ER, emergency room.

 The definitions provided in the table are taken from the FDA Guidance for Industry “Toxicity Grading Scale for Healthy Adults and Adolescent Volunteers Enrolled in Preventive Vaccine Clinical Trials” dated September 2007.

 Subject should be at rest for all vital sign measurements.

 Oral temperature; no recent hot or cold beverages or smoking.

 When resting heart rate is between 60 – 100 beats per minute. Use clinical judgment when characterizing bradycardia among some healthy subject populations, for example, conditioned athletes.

**Systemic AE Grading**

Systemic AEs	Mild (Grade 1)	Moderate (Grade 2)	Severe (Grade 3)	Potentially Life Threatening (Grade 4)
Diarrhea	2 – 3 loose stools or < 400 gms/24 hours	4 – 5 stools or 400 – 800 gms/24 hours	6 or more watery stools or > 800 gms/24 hours or requires outpatient IV hydration	ER visit or hospitalization
Headache	No interference with activity	Repeated use of non-narcotic pain reliever > 24 hours or some interference with activity	Significant; any use of narcotic pain reliever or prevents daily activity	ER visit or hospitalization
Malaise	No interference with activity	Some interference with activity	Significant; prevents daily activity	ER visit or hospitalization
Myalgia	No interference with activity	Some interference with activity	Significant; prevents daily activity	ER visit or hospitalization
Arthralgia	No interference with activity	Some interference with activity	Significant; prevents daily activity	ER visit or hospitalization
Nausea/ Vomiting	No interference with activity or 1 – 2 episodes/24 hours	Some interference with activity or > 2 episodes/24 hours	Prevents daily activity, requires outpatient IV hydration	ER visit or hospitalization for hypotensive shock

Systemic AEs	Mild (Grade 1)	Moderate (Grade 2)	Severe (Grade 3)	Potentially Life Threatening (Grade 4)
Seizures- <18 years of age; includes new or pre-existing febrile seizures	Seizure lasting < 5 minutes with < 24 hours postictal state	Seizure lasting 5 to < 20 minutes with < 24 hours postictal state	Seizure lasting $\geq$ 20 minutes OR > 24 hours postictal state	Prolonged and repetitive seizures (e.g., status epilepticus) OR Difficult to control (e.g., refractory epilepsy)

Abbreviations: ER, emergency room; IV, intravenous; PO, “per os” or oral administration.

 The definitions provided in the table are modified versions taken from the FDA Guidance for Industry “Toxicity Grading Scale for Healthy Adults and Adolescent Volunteers Enrolled in Preventive Vaccine Clinical Trials” dated September 2007 and DAIDS Table for Grading the Severity of Adult and Pediatric Adverse Events version 2.1 July 2017.

### Mali Laboratory AE Grading $\geq 15$ years of age

Hematology and Biochemistry Values 	Mild (Grade 1)	Moderate (Grade 2)	Severe (Grade 3)	Potentially Life Threatening (Grade 4)
Hemoglobin (Male) - gm/dL	9.5 – 10.3	8.0 – 9.4	6.5 – 7.9	< 6.5 and/or requiring transfusion
Hemoglobin (Female) gm/dL	8.0 – 9.0	7.0 – 7.9	6.0 – 6.9	< 6 and/or requiring transfusion
WBC Increase - 103/ $\mu$ L	11.5 – 15.0	15.1 – 20.0	20.1 – 25.0	> 25.0
WBC Decrease - 103/ $\mu$ L	2.5 – 3.3	1.5 – 2.4	1.0 – 1.4	< 1.0 with fever
Neutrophil/Granulocyte Decrease  - 103/ $\mu$ L	0.80 – 1.00	0.50 – 0.79	< 0.50	< 0.50 with fever
Platelets Decreased - 103/ $\mu$ L	100 – 110	70 – 99	25 – 69	< 25
Creatinine (Male) - $\mu$ mol/L	124.00 – 150.99	151.00 – 176.99	177.00 – 221.00	> 221.00 and requires dialysis
Creatinine (Female) - $\mu$ mol/L	107.00 – 132.99	133.00 – 159.99	160.00 – 215.99	> 216.00 and requires dialysis
Liver Function Tests/ALT - U/L	75.0 – 150.9	151.0 – 300.9	301.0 – 600.0	> 600.0

Abbreviations: ALT, alanine transaminase; WBC, white blood cell.

 The laboratory values provided in the tables serve as guidelines and are dependent upon institutional normal parameters. Institutional normal reference ranges should be provided to demonstrate that they are appropriate.

 The clinical signs or symptoms associated with laboratory abnormalities might result in characterization of the laboratory abnormalities as Potentially Life Threatening (Grade 4). For example, a low sodium value that falls within a grade 3 parameter should be recorded as a grade 4 hyponatremia event if the subject had a new seizure associated with the low sodium value.

 Note, neutropenias are graded and followed, but based on previous experience in African populations, should be interpreted with caution since lower values are more frequently observed in people of African descent.

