### 15.9.1 Pausing Rules for an Individual Subject

The pausing criteria for a SINGLE subject in this study include any of the following; note Year 1 and Year 2 will be evaluated independently given time between dosing:

- A subject experiences one SAE that is determined as possibly, probably, or definitely related to a study agent
- A subject experiences  $\geq 2$  Grade 3 or greater AEs that are deemed not to be a SAE (solicited local/systemic or unsolicited; lasting 48 hours or more) that are possibly, probably, or definitely related to a study agent, within the 7 days post vaccination
- A subject experiences  $\geq 2$  Grade 2 or greater laboratory abnormality (see [Appendix C](#)) or any Grade 3 or higher laboratory abnormality that are not deemed to be a SAE and are possibly, probably, or definitely related to the study agent, within the 7 days post vaccination
- $\geq 1$  subject experiences any local or solicited AE leading to hospitalization, or fever  $>40^{\circ}\text{C}$  ( $104^{\circ}\text{F}$ ) that is possibly, probably, or definitely related to the vaccine, or necrosis at the injection site, within the 7 days post vaccination
- Any safety issue that the site investigator determines should pause administration of a study agent to a single subject.

The CSO, in collaboration with the PI, may also pause for an individual subject if a safety concern is identified during routine aggregate data analysis.

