### Mali Laboratory AE Grading <15 years of age

Hematology and Biochemistry Values 	Mild (Grade 1)	Moderate (Grade 2)	Severe (Grade 3)	Potentially Life Threatening (Grade 4)
Hemoglobin (Male/Female) - gm/dL	7.5 – 8.4	6.1 – 7.4	5.0 – 6.0	< 5.0 g/dL
WBC Increase - 10^3/μL	14.5 – 16.0	16.1 – 20.0	20.1 – 30.0	>30.0
WBC Decrease - 10^3/μL	2.5 – 3.3	1.5 – 2.4	1.0 – 1.4	< 1.0 with or without fever
Neutrophil/Granulocyte Decrease - 10^3/μL	0.75 – 0.99	0.50 – 0.74	< 0.50	< 0.50 with fever
Platelets Decreased - 10^3/μL	100 – 120	70 – 99	25 – 69	< 25
Creatinine (Male/Female) - μmol/L	95.00 – 119.99	120.00 – 149.99	150.00 – 200.00	> 200.00 and requires dialysis
Liver Function Tests/ALT - U/L	75.0 – 150.9	151.0 – 300.9	301.0 – 600.0	> 600.0

Abbreviations: ALT, alanine transaminase; WBC, white blood cell.

 The laboratory values provided in the tables serve as guidelines and are dependent upon institutional normal parameters. Institutional normal reference ranges should be provided to demonstrate that they are appropriate.

 The clinical signs or symptoms associated with laboratory abnormalities might result in characterization of the laboratory abnormalities as Potentially Life Threatening (Grade 4). For example, a low sodium value that falls within a grade 3 parameter should be recorded as a grade 4 hyponatremia event if the subject had a new seizure associated with the low sodium value.

 Note, neutropenias are graded and followed, but based on previous experience in African populations, should be interpreted with caution since lower values are more frequently observed in people of African descent.

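### Appendix C gives no grade to creatinine above the Grade 3 cap without dialysis, or to afebrile WBC below 1.0 at 15 years or over, although milder values are Grade 3

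*Combined protocol and SAP*

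**What the plan says.** Appendix C has two Mali laboratory grading tables, one for 15 years or over and one for under 15.

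- **Creatinine, Grade 3 (μmol/L):** 177.00 to 221.00 (male, 15 or over), 160.00 to 215.99 (female, 15 or over) and 150.00 to 200.00 (under 15).
- **Creatinine, Grade 4, same order:** "> 221.00 and requires dialysis", "> 216.00 and requires dialysis" and "> 200.00 and requires dialysis".
- **Low WBC (10³/μL):** Grade 3 is 1.0 to 1.4 in both tables. Grade 4 is "< 1.0 with fever" at 15 or over, but "< 1.0 with or without fever" under 15.

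Other rows avoid the problem. Male hemoglobin Grade 4 at 15 or over is "< 6.5 and/or requiring transfusion". Neutrophil Grade 3 is open-ended below 0.50, with fever reserved for Grade 4.

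These grades are used elsewhere. Section 15.3 has laboratory AEs graded as Appendix C defines them. In the week after a dose, Section 15.9.1 pauses an individual on a single finding of this kind: "Grade 3 or higher laboratory abnormality that are not deemed to be a SAE and are possibly, probably, or definitely related". Sections 15.9.2 and 15.10 use percentages of participants at Grade 2 or above and Grade 3 or above. Section 15.12 stops vaccination after most related Grade 3 or higher AEs. Section 17.2.2 tabulates AEs by severity and allows a rank-test comparison of severity between arms.

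**The concern.** A severity scale should not lose a value because it got worse. Here the Grade 3 range has an upper limit, and the next cell adds a clinical condition that must also be met. A value past the limit that does not meet the condition falls between the two cells.

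Two things are at stake. First, such a value has no severity to enter in the safety tables or in a between-arm severity comparison; whatever grade it receives is undocumented and may differ between graders. Second, on a literal reading it does not count toward the laboratory pause and halt criteria or the related-AE withdrawal rule, although a milder value would.

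**Working it through.** **1. Literal lookup.** The cells were coded exactly as printed and test values were passed through them.

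| Row | Value | No dialysis / afebrile | Dialysis / fever |
|---|---|---|---|
| Creatinine, male ≥15 | 177, 221 | 3 | 3 |
| | 222, 331.5, 500 | none | 4 |
| Creatinine, female ≥15 | 160, 215.99 | 3 | 3 |
| | 216.00 | none | none |
| | 217, 324, 500 | none | 4 |
| Creatinine, <15 | 150, 200 | 3 | 3 |
| | 201, 300, 500 | none | 4 |
| WBC, ≥15 | 1.0, 1.2 | 3 | 3 |
| | 0.9, 0.5 | none | 4 |
| WBC, <15 | 0.9, 0.5 | 4 | 4 |
| Neutrophils, ≥15 | 0.4 | 3 | 4 |

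A female value of exactly 216.00 fits no cell even with dialysis, because Grade 3 ends at 215.99 and Grade 4 starts above 216.00.

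**2. Does other text supply the grade?** Footnote 1 says "The laboratory values provided in the tables serve as guidelines and are dependent upon institutional normal parameters" but gives no rule. Footnote 2 allows an upgrade to Grade 4 only when there are associated clinical signs or symptoms. Section 15.3.1 with Table 16, and the closing paragraph of Section 15.2, address items absent from the tables; creatinine and WBC are in them.

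**3. How abnormal is the creatinine gap?** Grade 3 limit (female: 216) divided by the Appendix D upper normal:

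- male: 221/98 = 2.26
- female: 216/72 = 3.00
- under 15: 200/48.9 = 4.09

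**4. How far does the neutrophil row cover WBC?** Neutrophils cannot exceed WBC. For an afebrile WBC below 1.0 at 15 or over, a neutrophil count below 0.50 is Grade 3, 0.50–0.79 is Grade 2, and 0.80–0.99 is Grade 1. Grade 3 is therefore missed only when WBC is 0.50–0.99 and neutrophils are at least 0.50. For example, WBC 1.2 with neutrophils 0.6 is Grade 3 on the WBC row, but WBC 0.9 with neutrophils 0.6 and no fever is only Grade 2, from the neutrophil row.

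**5. Counts needed for the group rules.** Participants with at least one dose (Section 3.3.1): 213 aged 5–8, 398 aged 9–18 and 490 aged 19 or over; total 213 + 398 + 490 = 1,101. Count = percentage × n, rounded up.

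- Age-group pause, Grade 3 or above, 5%: 10.65 → 11; 19.9 → 20; 24.5 → 25.
- Age-group pause, Grade 2 or above, 10%: 21.3 → 22; 39.8 → 40; 49.
- Halt, same Grade 3 or above, 10%: 110.1 → 111.
- Halt, same Grade 2 or above, 30%: 330.3 → 331.

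Dose-3 recipients (210, 386, 482; total 1,078) are an upper bound for Year 2. They give 10.5 → 11, 19.3 → 20 and 24.1 → 25 for the 5% pause, and 107.8 → 108 for the 10% halt. One ungraded value changes a group decision only if the count is otherwise exactly one short.

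**6. How often?** Section 3.3.1.4 reports one Grade 4 creatinine SAE, judged unrelated: 1/490 = 0.20% of adults, or 1/1,101 = 0.09% of vaccinees. It does not say whether dialysis or symptoms led to that grade, so it does not show how the gap is handled. The criteria cover 7 days after a dose, when normally one scheduled safety draw (day 3) falls.

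**The case against.** The best reply is that nobody grades by rigid lookup. Section 15.3 has the investigator assess severity for every AE, and records a diagnosis in place of the laboratory value where one is evident. A renal diagnosis would be graded on Table 16. A value that fits no cell could itself be read as not included in the appendix. Footnote 1 leaves room for judgement, and few investigators would leave creatinine 260 ungraded when 200 is Grade 3. The one relevant event on record did get Grade 4. Related SAEs trigger an age-group pause at one event and a halt at two, any safety issue can stop dosing, and Section 15.12 permits withdrawal for any AE in the participant's interest.

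Much of this stands as a limit on the effect. In practice a grade would often be supplied, and dangerous cases have other routes. But these routes rest on judgement and none fixes which grade applies. Appendix C is the stated definition for laboratory AEs, so two graders could reasonably differ on the same value.

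The timing point also reduces the effect. Section 3.3 gives the primary series as complete. Its stated date of 30 November 2020 does not fit Table 7, which puts vaccination between April and November 2019, nor the planned dose-4 accrual of June to October 2020. If dose 4 is also finished, the dosing rules have nothing left to act on, and only the severity tables remain.

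**Conclusion.** The point holds: four of the 16 laboratory rows are wrong as written, and the neighbouring rows show that the gap was avoidable. It is minor. It does not touch the primary endpoint, randomization, power or the efficacy analysis.

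For an individual, dose 4 is gated by the Year 2 exclusions in Section 9.10, which bar out-of-range creatinine or WBC unless judged not clinically significant and no worse than Grade 2. No study dose follows it, so a later individual pause or withdrawal has nothing to stop. What remains is the missing severity in the safety tables, and a missed count in the age-group pause and study-halt rules while others still await dose 4 (its window is ±112 days).

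This rests on reading the cells as printed, and on using participants with at least one dose as the denominator for the percentage rules. No ungraded value is shown to have occurred.

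**What to change.** Reword four Grade 4 cells:

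- Creatinine, male, 15 or over: `> 221.00 or requires dialysis`.
- Creatinine, female, 15 or over: `≥ 216.00 or requires dialysis`, which also closes the gap at exactly 216.00.
- Creatinine, under 15: `> 200.00 or requires dialysis`.
- Low WBC, 15 or over: below 1.0 regardless of fever, matching the under-15 table.

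For creatinine, an acceptable alternative is to leave Grade 3 open-ended (177.00, 160.00 and 150.00 or above) and keep dialysis for Grade 4, as the neutrophil row does with fever. Either works; the protocol should state one.

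Before the severity tables are made, search the laboratory data for values in these ranges and regrade any found, blind to arm.

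The cost is a wording amendment and one data query, with no new visits or blood draws. The downside is that a few more laboratory events may count toward a pause, halt or withdrawal.
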